16.0 APPENDIX 6: Immune reconstitution after chemotherapy with CPX-351

Immune reconstitution is believed to constitute a major element that determines the risk of relapse and the possibility of late infectious complications. Immune reconstitution after standard cytarabine and anthracycline combination has not been well studied and not at all after therapy with CPX-351. To this effect we propose the following:

To determine how CPX-351 influences the recovery of functional pathogen-specific and leukemia-specific immune responses.

We will conduct analyses of T cell phenotype, estimate antigen-specific T cell precursor frequencies (by intracellular cytokine flow cytometry and peptide/dextramer staining) and determine antigen-specific cytokine production capacity (cytokine bead array assay). We will evaluate antigen-specific T cell recovery following treatment with CPX-351 by analyzing 1) Immunophenotypic recovery of Th1, Th2, Th17 and regulatory T cells; 2) The number and function of recovering CMV and Flu-specific T cells capable of responding functionally to in vitro stimulation with overlapping pools of peptide by intracellular cytokine detection; 3) The number and function of T cells capable of responding to leukemia-associated antigens including proteinase 3 (PR3), Wilms tumor antigen (WT1) and cancer testis antigens (e.g. PRAME) will be assessed following stimulation with overlapping pools of peptide and intracellular cytokine assay.

To determine how CPX-351 influences the recovery and function of NK cells

To evaluate if CPX-351 will impact on NK phenotype and function, we will conduct longitudinal analyses of NK phenotype and function during CPX-351 therapy.

Quantitative 10-color flow cytometric analysis will be performed to 1) characterize the functional phenotype of NK cells using an extended panel of antibodies against activating (NKp30, NKp44, NKp46, NKG2D, NKG2C, DNAM1) and inhibitory receptors (NKG2A and KIRs); 2) assess the effector function of NK product against MHC class I-deficient leukemia targets and primary AML cells from the recipient by intracellular cytokine assay for interferon-gamma (IFN- γ) production, chemokine production including CCL3 (MIP1 α) and CCL4 (MIP1 β) and cytotoxicity, including CD107a degranulation and 51chromium release assay; Confocal microscopy will be used to directly assess the immune synapse formation with leukemia targets.

Sample collection and distribution

60 cc of blood (Green top tubes- heparin) and 5 cc in purple top (EDTA) to be collected at 3 time points:

- 1- Before induction with CPX-351
- 2- At recovery from induction, just prior to consolidation #1
- 3- At recovery from 1st cycle of consolidation just prior to consolidation #2

Samples will be sent to [name] lab manager, P14.3144; [contact].

17.0 APPENDIX 7: Early Detection of CPX-351-induced cardiotoxicity using high sensitivity troponin T

Chemotherapy is an effective treatment in most cancers. Yet all these drugs have a various range of side effects. Chemotherapy-induced organ injury remains a major issue in cancer patient care. Chemotherapy-induced cardiotoxicity is the most serious one, particularly associated with the use of anthracyclines, ultimately impacting the long-term cancer survivors and survival time. CPX-351 is a liposomally encapsulated combination of cytarabine and daunorubicin. The liposomal encapsulation may lead to a decrease in cardiac toxicity. However, the CPX-351-induced cardiotoxicity has not been evaluated.

Identification of chemotherapy-induced cardiac toxicity has been dependent on imaging modalities, such as echocardiogram or MUGA scan. Despite their usefulness, routine cardiac imaging alone lacks sensitivity for early detection of subclinical cardiac disease. Multiple cardiac biomarkers have been evaluated extensively in both animal models and clinical studies such as creatine kinase (CK), creatine kinase – MB fraction (CK-MB), troponin T (cTnT), troponin I (cTnI), brain natriuretic peptide (BNP), C-reactive protein (CRP), and interleukin family member (ST2).^{5, 6} In acute coronary syndromes, troponin is one of the most well established biomarkers used to guide diagnosis and treatment. However, the utility of biomarkers in monitoring myocardial damage secondary to chemotherapy is still controversial.

Both cTnT and cTnI have been demonstrated in multiple clinical studies to be sensitive and specific markers for detecting myocardial injury after chemotherapy administration. The level of troponin released into circulation has a good predictive value for subsequent decrease in LV ejection fraction and adverse cardiac events long before the impairment is observed by echocardiogram or symptoms have developed. Elevation in troponin has shown a positive predictive value of 50-84%, and a negative predictive value of 90-99%.^{5, 7} Furthermore, the peak value and the duration of elevated troponin level have a strong relationship with the degree of LV dysfunction. In contrast, BNP, NT-proBNP, CK, CK-MB and CRP have shown to be less sensitive and specific in detecting subclinical heart failure in this group of patients.^{8, 9}

Recent advances in assay technology have led to more sensitive and precise cardiac troponin T assays that can detect TnT level as low as 0.005 µg per liter.¹⁰ With increasing in sensitivity, high-sensitive troponin T (hs-TnT) has superiority over standard troponin test in early diagnosis of acute myocardial infarction.¹¹ In chronic stable angina, higher levels of hs-TnT has been shown to be associated with the higher incidence of cardiovascular death and heart failure in the future.¹² Recently, hs-TnT has been evaluated as a peri-operative risk stratification in non-cardiac surgery patients.¹³ Interestingly, they found that hs-TnT level above universal cut-off were associated with a 2.6-fold increase in in-hospital mortality and morbidities from cardiovascular system.

To our knowledge, no prior study has ever evaluated hs-TnT during CPX-351 chemotherapy administration. Therefore, our primary objective is to assess whether hs-TnT obtained during the course of CPX-351 chemotherapy could allow us to monitor the development of acute cardiotoxicity.

- Primary objective:

To test the feasibility of using high-sensitivity troponin T to monitor acute CPX-351-induced cardiotoxicity. In addition, BNP and cardiac troponin I will be measured.

- Roche high sensitivity troponin T assay is a sandwich chemiluminescent assay. High sensitivity troponin T assay gives detection limit of 5 ng/L and the 99th percentile of cutoff 14 ng/L. It can be run on MODULAR ANALYTICS E170, Elecsys 2010, cobas e411, cobas e 601 and cobas e 602 analyzers.
- This high sensitivity troponin T assay will be measured on Cobas e601 using Roche reagents including calibrators and controls.

Sample collection and distribution

3 cc of blood (Green top tubes- heparin) at the following time points:

- 1- Before the start of each cycle with CPX-351 (baseline)
- 2- Approximately 24 hrs after the end of the first dose (Day 1 + 1) (for each cycle)
- 3- Approximately 25 hrs after the end of the dose given on day 5 (Day 5 + 1) (for each cycle)
- 4- Approximately on day 14 (± 4 days) for each cycle
- 5- End of treatment

Samples will be sent to [name] lab, on R4.1446, Clinical Chemistry Laboratory, Department of Laboratory Medicine; c/o [name], [contact]; [contact]; email: [contact].

18.0 APPENDIX 8: Pharmacodynamic Investigations During CPX-351 Therapy

The objectives of the pharmacokinetic and pharmacodynamic investigations during this clinical trial are as follows:

- (1) To test ex vivo cytotoxicity of combination of Pim kinase inhibitor(s) and CPX-351 on circulating leukemia cells.
- (2) To investigate effect of Pim kinase inhibitor on phosphorylated and total protein levels in pim kinase signaling pathway.

Only patients entering at MD Anderson Cancer Center will be studied. All patients with >5,000 WBC/ μ l of peripheral blood will be requested to participate in the cellular pharmacodynamics studies. Patients will sign consent forms to enter these investigations.

Once a patient has consented to participate in the investigation, please contact [name] ([contact]) or [name] ([contact]) in The Laboratory of Cellular and Molecular Pharmacology ([name], phone, [contact]) to coordinate scheduling of blood samples. To facilitate preparedness for laboratory studies, please plan on initiating therapy in the subsequent morning if the clinical situation allows and please inform us as soon as there is a possibility of patient entering the clinical trial.

Blood samples will be collected at the following times from patients in the Dose Escalation Phase: Total of 2 samples will be collected.

Cycle 1.	Day 1: 0 (pre-dose), 24 h	Two green top tubes (2 \times 10mL) One green top tube (1 \times 10mL)
-----------------	------------------------------	---

For the pre-dose (sample 1), two tubes of blood (10mL each) will be collected in a Vacutainer green top tube. For the remaining sample (sample 2), one tubes of blood (10mL) will be collected in a Vacutainer green top tube. The samples will be mixed and immediately put on ice-bath. Samples will be brought to [name] laboratory in the Tan zone (T1.3839). The blood will be centrifuged and plasma will be separated, transferred to storage tubes and immediately frozen, and stored until analysis. After removal of plasma, the blood cells will be resuspended in PBS and AML blasts will be isolated by Ficoll-Hypaque density-gradient centrifugation procedures. Cells will be used for the following laboratory endpoints.

NOTE: We may not be able to do all studies in every patient. This will be decided based on diagnosis and number of leukemia cells recovered from the peripheral blood sample.

Effect of ex-vivo combination with Pim kinase inhibitors on AML blasts during CPX-351 therapy: Pre-treatment leukemia cells or cells isolated during CPX-351 therapy will be cultured ex-vivo with varying concentrations of Pim kinase inhibitors to evaluate the effect of combined DNA damage and anthracyclines with Pim kinase inhibition on AML blasts.

Induction of apoptosis will be measured using flow cytometric analysis of Annexin-V and PI binding assay. Cells will be saved as pellets for future testing of phosphorylated and total protein levels in pim kinase signaling pathway.

19.0 APPENDIX 9: AML with MDS-Associated Karyotype

With myelodysplastic syndrome-related cytogenetic abnormalities:

- Complex karyotype (defined as 3 or more chromosomal abnormalities).
- Unbalanced: -7 or del(7q); -5 or del(5q); i(17q) or t(17p); -13 or del(13q); del(11q); del(12p) or t(12p); del(9q); idic(X)(q13).
- Balanced: t(11;16)(q23;p13.3); t(3;21)(q26.2;q22.1); t(1;3)(p36.3;q21.2); t(2;11)(p21;q23), t(5;12)(q33;p12); t(5;7)(q33;q11.2); t(5;17)(q33;p13); t(5;10)(q33;q21); t(3;5)(q25;q34)

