3.0 Study Objectives and Rationale

3.1 Primary Objectives

The primary objective of this study is to assess preliminary efficacy (as determined by the rate of CR or CRI) of two or three dose levels of CPX-351 in patients with newly diagnosed AML at high risk for induction mortality, defined as 30-50% predicted risk of death by Day 60, and to select the most promising dose level for further efficacy testing. Estimation of risk for induction mortality at patient screening will be based on factors associated with lower likelihood of AML response with or without factors that reduce tolerance to treatment-associated adverse events.

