5.0 Selection and Withdrawal of Patients

5.1 Study Population

5.1.1 *Inclusion criteria*

- 5.1.1.1 Ability to understand and voluntarily sign an informed consent form
- 5.1.1.2 Age ≥ 18 years at the time of diagnosis of AML
- 5.1.1.3 Pathological diagnosis of AML according to WHO criteria (with at least 20% blasts in the peripheral blood or bone marrow):
 - Newly Diagnosed De novo AML; except for APL
 - Newly Diagnosed Secondary AML, defined as having a history of an antecedent hematologic disorder (myelodysplastic syndromes [MDS], myeloproliferative disease [MPD] or history of cytotoxic treatment for non-hematologic malignancy) or apparent de novo AML with MDS-associated karyotype. (Appendix 9)
- 5.1.1.4 Eastern Cooperative Oncology Group (ECOG) performance status 0-3
- 5.1.1.5 Laboratory values fulfilling the following:
 - Serum creatinine ≤ 2.0 mg/dL
 - Serum total bilirubin ≤ 2.0 mg/dL
 - Serum alanine aminotransferase < 3 times the ULN Note: If elevated liver enzymes are related to disease ALT should be < 5 times ULN.
- 5.1.1.6 To be considered at high risk for induction mortality patients must have 1 or 2 of the following risk factors (patients ≥ 60 must have at least 1 risk factor, patients < 60 must have at least 2 risk factors) present. At least one risk factor in every patient must be an AML-related factor:
AML-related factors include:
 - AHD (MDS, CMML, or MPD) or history of exposure to cytotoxic chemotherapy (t-AML), or WHO-defined AML with MDS-related changes or apparent de novo AML with MDS-associated karyotype.
 - Unfavorable cytogenetics as defined by the European Leukemia Net (Appendix F) Appendix 11

Patient-related factors:

- Age ≥ 70
- ECOG PS ≥ 2
- Co-morbidities: Serum creatinine >1.3 g/dL

5.1.1.7 Cardiac ejection fraction $\geq 50\%$ by echocardiography or MUGA (when LVEF expressed as a range, at least the upper limit should include 50%).

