20.0 APPENDIX 10: European Leukemia Net (ELN) Classification

Table 4. Standardized reporting for correlation of cytogenetic and molecular genetic data in AML with clinical data

Genetic group	Subsets
Favorable	t(8;21)(q22;q22); RUNX1-RUNX1T1 inv(16)(p13.1q22) or t(16;16)(p13.1;q22); CBFB-MYH11 Mutated NPM1 without FLT3-ITD (normal karyotype) Mutated CEBPA (normal karyotype)
Intermediate-I*	Mutated NPM1 and FLT3-ITD (normal karyotype) Wild-type NPM1 and FLT3-ITD (normal karyotype) Wild-type NPM1 without FLT3-ITD (normal karyotype)
Intermediate-II	t(9;11)(p22;q23); MLLT3-MLL Cytogenetic abnormalities not classified as favorable or adverse†
Adverse	inv(3)(q21q26.2) or t(3;3)(q21;q26.2); RPN1-EVI1 t(6;9)(p23;q34); DEK-NUP214 t(v;11)(v;q23); MLL rearranged –5 or del(5q); –7; abnl(17p); complex karyotype‡

Frequencies, response rates, and outcome measures should be reported by genetic group, and, if sufficient numbers are available, by specific subsets indicated; excluding cases of acute promyelocytic leukemia.

*Includes all AMLs with normal karyotype except for those included in the favorable subgroup; most of these cases are associated with poor prognosis, but they should be reported separately because of the potential different response to treatment.

†For most abnormalities, adequate numbers have not been studied to draw firm conclusions regarding their prognostic significance.

‡Three or more chromosome abnormalities in the absence of one of the WHO designated recurring translocations or inversions, that is, t(15;17), t(8;21), inv(16) or t(16;16), t(9;11), t(v;11)(v;q23), t(6;9), inv(3) or t(3;3); indicate how many complex karyotype cases have involvement of chromosome arms 5q, 7q, and 17p.

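### Two definitions of complex karyotype feed one eligibility criterion with no precedence, so AML that Appendix 10 classes as Favorable can qualify as high-risk through Appendix 9

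*Combined protocol and SAP*

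**What the plan says.** Section 5.1.1.6 requires at least one AML-related factor in every patient. Two of the routes to that factor are karyotypic:

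- "apparent de novo AML with MDS-associated karyotype", which Section 5.1.1.3 ties to Appendix 9;
- "Unfavorable cytogenetics as defined by the European Leukemia Net", for which the ELN table is Appendix 10.

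On the number of factors, "patients ≥ 60 must have at least 1 risk factor"; younger patients need two.

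The appendices differ on what is complex. Appendix 9 has "Complex karyotype (defined as 3 or more chromosomal abnormalities" with no condition, and it also lists single lesions such as del(9q) without condition. The Appendix 10 footnote has "Three or more chromosome abnormalities in the absence of one of the WHO designated recurring translocations or inversions", and it names t(8;21), inv(16)/t(16;16) and t(9;11) among those exceptions. The Appendix 10 table puts t(8;21) and inv(16)/t(16;16) in the Favorable group and t(9;11) in Intermediate-II.

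The only genetic exclusion is in Section 5.1.1.3: "Newly Diagnosed De novo AML; except for APL". Section 3.1 bases the risk estimate on "factors associated with lower likelihood of AML response".

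**The concern.** The same karyotype can be high-risk under one appendix and Favorable under the other, and 5.1.1.6 takes whichever route admits the patient. Such a patient does not fit the population described in Section 3.1, which is selected for a poor chance of response and a predicted 30-50% risk of death by Day 60.

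What could be at stake is the reading of CR+CRi in small arms. Section 4.0 calls an arm with 3 or fewer responses in 15 non-efficacious, and Section 10 chooses the dose with the highest response rate, subject to toxicity. One responder is 1/15 = 6.7 percentage points. A patient whose better prognosis comes from the karyotype could therefore bear on a decision for reasons unrelated to dose.

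**Working it through.** **Step 1: does the text admit such a patient?** Take a patient aged 60 or over with t(8;21) and two further abnormalities, and no antecedent disorder or prior cytotoxic therapy.

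| Rule | Result |
|---|---|
| Appendix 10 footnote | Not complex, because t(8;21) is present |
| Appendix 10 table | Favorable |
| Appendix 9 | Complex, so MDS-associated karyotype |
| 5.1.1.6 | AML-related factor met; one factor is enough at this age |
| 5.1.1.3 and 5.1.2 | No genetic exclusion other than APL |

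The result is the same for inv(16)/t(16;16) plus two abnormalities, and for t(8;21) plus del(9q). Section 5.1.1.6 lists the MDS-associated karyotype as an alternative in "WHO-defined AML with MDS-related changes or apparent de novo AML with MDS-associated karyotype", so any order of precedence within the WHO scheme is not brought in. Of the abnormalities in the footnote, only t(8;21) and inv(16)/t(16;16) are Favorable. t(9;11) is Intermediate-II; t(v;11), t(6;9) and inv(3)/t(3;3) are Adverse in any case; t(15;17) falls under the APL exclusion.

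**Step 2: reproduce the plan's figure.** Section 10 tests 5% against 30% with 15 patients and states 87% power at one-sided 0.05. Rejecting at 3 or more responses, the exact binomial gives P(X ≥ 3 | 15, 0.05) = 0.036 and P(X ≥ 3 | 15, 0.30) = 0.873. The stated power is confirmed.

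**Step 3: effect if one such patient is in the arm.** Let q be that patient's chance of response. The documents do not give q; 0.5 to 0.9 is assumed. The other 14 respond at rate p.

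P(X ≥ k) = q·P(Y ≥ k−1) + (1−q)·P(Y ≥ k), with Y binomial(14, p).

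- p = 0.20, k = 4: P(Y ≥ 3) = 0.552 and P(Y ≥ 4) = 0.302. With no such patient, P(X ≥ 4 | 15, 0.20) = 0.352. With q = 0.5, 0.8 and 0.9 it is 0.427, 0.502 and 0.527.
- p = 0.05, k = 3: P(Y ≥ 2) = 0.153 and P(Y ≥ 3) = 0.030. With no such patient it is 0.036. With q = 0.5, 0.8 and 0.9 it is 0.092, 0.128 and 0.141.

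**Step 4: effect averaged over how often such a patient enters.** The documents give no frequency in this population. Study 205, in first-relapse AML, reports t(8;21), inv(16) or t(16;16) in (7+4+2+1)/125 = 11.2%. Assume 3% to 11.2% of candidates carry one of these and 10% to 30% of those have qualifying extra abnormalities. The entry frequency f then runs from 0.03 × 0.10 = 0.3% to 0.112 × 0.30 = 3.4%. Over 80 patients that is 0.24 to 2.7 expected entrants, and the chance of at least one in a 15-patient arm, 1 − (1−f)^15, is 0.04 to 0.40.

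With q = 0.8 the average response rate is p(1−f) + 0.8f:

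- p = 0.20: 0.2018 to 0.2202, so P(X ≥ 4 | 15) is 0.359 to 0.428, against 0.352.
- p = 0.05: 0.0523 to 0.0752, so P(X ≥ 3 | 15) is 0.040 to 0.098, against 0.036.

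**Step 5: DLT.** Section 4.0 accepts fewer than 5 DLTs in 15. Assume the other 14 patients have a 33% DLT risk and the one patient 5% to 20%. The expected rate moves from 33% to (14 × 0.33 + 0.05)/15 = 31.1% at one end and (14 × 0.33 + 0.20)/15 = 32.1% at the other. P(fewer than 5) moves from 0.415 to between 0.44 and 0.475. Both the size and the direction rest on the assumed risk.

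**The case against.** The strongest reply is that the two appendices serve different purposes. Appendix 9 describes a disease category and Appendix 10 a prognostic group, so a difference between them is not in itself an error. Appendix 9 already admits karyotypes that ELN does not call adverse, such as isolated del(13q) or del(9q). A plain count also has precedent in the documents: Study 204 stratified at three abnormalities, and the 998-patient analysis in Section 2.1 names complex karyotype as an early-mortality factor, with no exclusion stated in either place. This stands, and it is why t(9;11) should be left alone. It does not cover a karyotype that the protocol's own table calls Favorable.

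Second, Section 4.0 asks for a predicted 30-50% risk, and the screening table in Section 6.1 records the basis for it. An investigator could decline such a patient on those grounds. These are soft checks: 5.1.1.6 is the only place where the risk is made operational, and it does so through the factor list.

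Third, the figures in Step 3 presuppose that such a patient is present and ignore interim stopping. With the Table 7 futility stops and one patient at 80% in a random position, the 5% case goes from 0.024 to 0.085 rather than from 0.036 to 0.128. In the 100 units/m² arm of up to 40, one responder is 2.5 points. Between the 50 and 75 units/m² arms, randomization balances such patients in expectation. All of this stands and limits the size.

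A reader might infer that the primary response and DLT rates are in fact distorted. The documents do not support that: they give no count, response rate or DLT rate for these patients.

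**Conclusion.** The gap in the eligibility definition is real and can be checked on the page: two unequal definitions, one criterion, no precedence, and a literal route by which Favorable AML is labelled high-risk. Its effect on CR+CRi is possible, not demonstrated. Given one such patient in 15, the chance of passing the 3/15 cut at a true 20% goes from 0.35 to 0.43-0.53 under an assumed response of 50-90%. Averaged over an assumed entry frequency of 0.3-3.4% with 80% response, it goes to 0.36-0.43. The upper end relies on a frequency from relapsed disease, and neither range allows for the second factor required below age 60. The DLT effect of one patient is about 1 to 2 points under an assumed benefit, which is not material. Sample size, type I error and power are unaffected. The point is worth correcting because following the stated rule admits patients outside the intended population and the remedy is small.

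**What to change.** Reconcile the two definitions. In 5.1.1.6 or Appendix 9, state that an Appendix 9 karyotype does not by itself count as an AML-related factor when Appendix 10 classes the disease as Favorable by t(8;21) or inv(16)/t(16;16). Wording it this way also covers single lesions such as del(9q), which a change to the complex-karyotype line alone would leave open. Entry through an antecedent hematologic disorder or therapy-related AML stays as it is, and so does t(9;11).

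In Section 10, add one line: report CR+CRi and DLT rates with and without any ELN-Favorable patients already enrolled. This carries into the analysis the Appendix 10 instruction to report by genetic group, which Section 10 does not take up.

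The cost is one sentence, one sensitivity line and the loss of very few otherwise eligible patients. The planned numbers, type I error and power do not change.
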